#### **T. Withdrawal/Early Withdrawal**

1. Describe how and when a subject may withdrawal from the study. **A participant may withdraw at any time by simply indicating to anyone in the research team that they no longer wish to participate. Subjects will be provided with the Revocation of HIPAA Authorization form.**
2. Provide procedures for the orderly termination of participation by the participant and if any consequences would result from early withdrawal from the study. **Upon the participant informing us they no longer wish to participate, they will be removed from active status on the study. There are no consequences to early withdrawal.**
3. Explain if survival data is required. If so, clarify how data will be obtained. **N/A**
4. Not Applicable; subjects not recruited; chart review.

#### **U. Risk/Benefit Assessment**

1. **Potential Study Risks**
  - 1.1. Describe and assess all of the following risks that may be associated with the research:
    - 1.1.1. **Physical There is a small chance of mild pain and swelling where the needle enters the skin and vein, bruising, infection and possibly fainting during the blood draws at baseline and 18 months. Texting (reading and sending) while driving may potentially lead to automobile accidents and bodily injury.**
    - 1.1.2. **Psychological There is a small chance that talking about their personal history can be embarrassing and/or lead to psychological discomfort.**
    - 1.1.3. **Social There is slight risk of embarrassment in terms of coming to the MIRECC suite for the research as MIRECC is geared towards research with mental illness and the stigma associated with mental illness.**

- 1.1.4. Economic **There is no foreseeable economic risk to participation.**
- 1.1.5. Monetary **The Veteran will not have to pay for treatment or participation but will need to pay for transportation to get to the research visits.**
- 1.1.6. Legal **There is no foreseeable legal risk associated with the research. In Pennsylvania it is illegal to text while driving.**
- 1.1.7. Loss of confidentiality **In all research, indeed in all situations, there is a risk of a loss of confidentiality. For instance, if the participant does not have a password on their phone, anyone could pick up their phone and be able to read their confidential messages. This is of incredible importance to the research team and confidentiality will be closely guarded. We will guard participants' information through secure servers (for web-based data) and in locked cabinets in with the MIRECC suite (for paper-based data). In addition, there is the risk that a person authorized to access the text messages might use them for an unauthorized purpose or disclose them to an unauthorized party.**
- 1.1.8. Assess the likelihood and seriousness of such risks. **Low.**
- 1.1.9. Other **N/A**

- 1.2. Specify what steps will be taken to minimize these risks. **Research staff is trained in the proper use and storage of confidential information as well as not to disclose information over the phone. Research staff is also trained in proper interviewing methods and how to handle delicate questions (such as questions regarding PTSD, etc). We have clinicians on hand at the VA who can speak with any Veteran who has experienced discomfort as a result of the research visit. We will attempt to schedule research visits on days that the Veteran has another appointment scheduled to minimize travel costs. Participants will be reminded of the risk of texting while driving and will affirm that they will not engage in this behavior with their signature on the consent form.**
- 1.3. If methods of research create potential risks, describe other methods, if any, that were considered and why they will not be used.
- 1.4. If chart review, breach of confidentiality is always a concern. Specify what steps will be taken to minimize these risks.

## 2. Potential Study Benefits

- 2.1. Assess the potential benefits to be gained by the individual subject, as well as benefits that may accrue to society in general as a result of the planned work. **The project will yield considerable information on whether a prevention intervention can help Veterans who are receiving prescription opioids daily and engaging in risky drinking reduce their drinking to below risky levels and sustain those improvements for 18 months. Information will also be obtained regarding moderators and mediators of intervention effects that are obtained. This information will be of direct value to VA treatment providers who are working with Veterans on prescription opioids and trying to reduce their risk for poor outcomes. Ultimately, the availability of effective prevention interventions will benefit Veterans on prescription opioids who are engaging in risky drinking.**
- 2.2. If the subject does not receive any direct benefit, then it must be stated here and in the consent form. **The subject may not receive any direct benefit from the study.**

## 3. Alternate Procedures

- 3.1. Describe the alternatives available to the subject outside the research context. **The alternative is VA's usual care which includes a brief intervention aimed at reducing drinking.**
- 3.2. If none, state that the alternative is not to take part in this research study at all.

**V. Data and Safety Monitoring Board (DSMB) or Data Monitoring Committee (DMC) (All Phase III studies are required to have a DSMB. However, the IRB has the right to require a DSMB with any study.)**

1. **Will an independent DSMB or DMC oversee the project?**  YES  NO  N/A  
2.1. If yes, please provide contact information for the DSMB or DMC or Coordinating Center Representative and attach a copy of the charter.

Name:

Phone Number:

Title:

E-mail:

2. **If a DSMB or DMC will not monitor this study, who will monitor this study? Check all that apply.**

Principal Investigator  
 Sponsor  
 VA Cooperative Studies Program  
 Safety monitoring committee

**W. Data Monitoring** (*Monitoring plans describe how a monitor, independent of the study team, regularly inspects study records to ensure the study is adhering to the study protocol and applicable research regulations and CMCVAMC requirements. Monitoring plans do not necessarily require the use of an independent Data and Safety Monitoring Board (DSMB). Such independent boards are usually reserved for high-risk phase I studies, or large, multi-center phase III trials. Federally funded studies may require the use of an independent DSMB.*)

1. **Describe the data monitoring plan.** (All protocols must have a data monitoring plan appropriate for the potential risks and the complexity of the study.) **Data will be collected using standardized forms and will only be identified with the study's ID of the participant.** The codes that link the name of the participant and the study ID will be kept confidential by the project coordinator in a secured cabinet at CMCVAMC. Most of the study data will be entered directly into databases as it is collected, via an intranet-based data entry system at the CMCVAMC. Data forms that are not amenable to web-based data entry will be entered by the research staff, and discrepancies will be corrected by a supervisor, based on source documents. The quality of the data will be monitored once per month. The study's statistician will analyze the data, using SAS and SPSS software.

The primary outcome measure will be rates of risky drinking (i.e., more than 4 drinks at any one sitting or more than 14 drinks/week for men; more than 2 drinks at any one sitting or more than 7 drinks/week for women) within each follow-up period (e.g., months 1-3, 4-6, 7-9, 10-12, 13-18), as determine by the TLFB. Secondary outcomes in the study will be self-reported frequency of heavy drinking days (TLFB), biological measures of alcohol use (%dCDT and GGT), urine toxicology tests to assess other drug use, VA medical records of opioid overdoses, depression, and pain. Outcome data will be analyzed using mixed effect regressions for continuous and categorical data (i.e., SAS) and various packages to examine mediation effects (i.e., MPlus). The alpha level for the primary outcome will be set at 5%.

Data quality will be monitored by random inspection of the completed forms by the research coordinator and any problems detected will be discussed with the PI. The Research prevention counselors will receive standardized training on the interventions, which are all manualized. Adherence to the manuals will be monitored using audiotapes and individual supervision provided by the clinical coordinator. If drift is observed the counselors will be re-trained.

Blind interim analyses of the data will be conducted at two points when 50 and 75% of the sample has been accrued. If the results show statistically overwhelming significant differences between groups, the study will be stopped (or one of the conditions stopped).

2. Describe how protocol deviations, adverse events, serious adverse events, breaches of confidentiality, unanticipated adverse device effect (UADE), and unanticipated or unexpected problems will be reported to the CMCVAMC IRB and sponsor. (Refer to the CMCVAMC Standard Operating Procedure (SOP) Manual for reporting guidelines.) In this study we will use the FDA definition of serious adverse events (SAEs). SAEs will be systematically assessed at each clinic visit. Any SAE, whether or not related to study intervention, will be reported to the IRB and DoD. The initial SAE report will be followed by submission of a completed SAE report to both institutions. In the event that a participant either withdraws from the study or the investigator decides to discontinue a participant due to SAE, the participant will be monitored by the investigator via ongoing status assessment until either a resolution is reached (i.e., the problem requiring hospitalization has resolved or stabilized with no further changes expected), the SAE is determined to be clearly unrelated to the study intervention, or the SAE results in death. Unanticipated problems involving risk to volunteers or others, serious adverse events related to participation in the study and all volunteer deaths related to participation in the study should be promptly reported by [contact]), by e-mail ([contact]), or by [contact]) to the U.S. Army Medical Research and Materiel Command's Office of Research Protections, Human Research Protections Office. A complete written report should follow the initial notification. In addition to the methods above, the complete report can be sent to the U.S. Army Medical Research and Materiel Command, ATTN: MCMR-RPH, [name].

**Additionally, SAE's, protocol deviations, breaches of confidentiality and unanticipated or unexpected problems will be reported to the VA IRB within five days of discovery.**

2.1. Describe the management of information obtain that might be relevant to participant protections such as:

- 2.1.1. Unanticipated problems involving risks to subjects or others – **These will be reported to IRB within five days of discovery just as SAEs.**
- 2.1.2. Interim results – **Will be report these at continuing review.**
- 2.1.3. Protocol modifications – **Will be proposed to the IRB and practices will not change until the modifications are approved by the IRB.**

3. If applicable, define the plan for subjects if research shows results such as:

- 3.1. Depression If depression appears to be an issue for a participant, and they are not already receiving treatment, the research staff will consult with [name] for a consult with the participant and a possible referral.
- 3.2. Suicide Participants who indicate any suicidal ideation will be evaluated by [name], [name], or [name] at the CMCVAMC.
- 3.3. Abuse It is anticipated that the Veterans in our study will be engaging in alcohol or drug abuse. [name] will be consulted in the event there is significant change to the Veterans' use status. If the Veteran is in danger in terms of physical abuse or someone else is in danger due to the Veteran abusing them, [name] will be consulted and the appropriate actions will be taken.

4. Statistical Analysis

- 4.1. Include statistical power calculations and the assumptions made in making these calculations. **We consider the primary hypothesis of risky alcohol use, which compares PI and BIO groups on five repeated binary outcomes. We use the sample size formulae of Diggle et al. We expect to have a 20% dropout rate by month 18, and to see a risky drinking rate of 30%. On the assumption of a within subject correlation of 0.3 (resp. 0.4, 0.5), our sample size of 150 per group provides 80% power for a main effect difference of 30% versus 20% (resp. 30% versus 19%, 30% versus 18%) for the BIO versus PI groups.**

**March 2018 Amendment:** Our original power analysis in the grant was very conservative, as it took into account multiple outcome measures and moderation and mediation analyses. We had our statistician re-run the analyses, focusing on the main effect treatment group comparison with the primary outcome measure. If we calculate sample size needed to have 80% power to find a 15- percentage point difference in rates of risky drinking between the two conditions (e.g., 35% control condition vs. 20% experimental condition on risky drinking rate), we need a total of 136 to 162 veterans (depending on different estimates of the correlation between the outcome measure at different follow-up points). If the effect is slightly larger (e.g., 20 percentage point difference), we only need 72 to 84 veterans in total. Therefore, with a combination of the new design we are confident that we will reach a sample size that will be sufficient to at least examine our primary outcome measure.

- 4.2. Define plans for data and statistical analysis, including key elements of the statistical plan, stopping rules and endpoints.
  - a. Primary objective: The responses for the primary hypothesis comprise five repeated binary measurements per participant indicating risky alcohol use over the follow-up points. Our main analyses will use mixed effects logistic regression models to compare the two groups on the rates of risky alcohol use. We expect that linear and quadratic trends will account for the patterns of use across time. If residual analyses suggest significant lack of fit, we will examine more general time trends using spline specifications. The main explanatory variable will be a binary factor indicating intervention group, together with terms for time trends, and for group by time interactions, if appropriate. Based on analyses of similar data, we expect that a random intercept model, possibly with an autoregressive repeated measures structure, should provide a good fit to the covariance structure of the repeated measures, although we will examine more general specifications, if necessary. The estimated regression coefficients for the group variable, and possibly for group by time interactions, will address our primary hypothesis. We will test whether estimated coefficients are different from zero, and will report estimates and approximate 95% confidence intervals.
  - b. Secondary outcomes. For Hypothesis 1, we will use the same type of mixed effects logistic regression models as described above to compare the groups on urine toxicology tests for use of drugs other than alcohol. The frequency of heavy drinking is a count response, so we will use mixed effects Poisson regression models to compare two groups on the number of heavy drinking days in a week. The models will allow for over dispersion by including estimation of a variance inflation factor or, if this is insufficient, by considering mixed effects negative binomial regression models. Some subjects have more days without heavy drinking than would be expected under a Poisson model. To account for this, we will fit mixed effects zero inflation models. If levels of heavy drinking are too low even for zero-inflation models, we will compare the intervention groups on the absence or presence of any heavy drinking days in a week, using mixed effects logistic regression models. Measures of depression and pain, and biological measures of alcohol use, will be continuously distributed, and will be compared across the groups using mixed effects linear regression models, after transformation of these responses to approximate normality. The explanatory variables, time trends, and covariance structure for these secondary analyses will be chosen as described for the primary hypothesis.

We will follow a similar approach for testing Hypothesis 2, using data generated by electronic medical records to count the number of opioid overdoses for each participant through the course of the trial. We expect low rates of OD, so we will compare the groups on the rates of having an OD via a logistic regression model. If the numbers of OD are sufficiently high, we will compare the groups using Poisson or Negative Binomial models for the total number of OD per participant across the trial.

c. Moderator analyses. We will address Hypothesis 3 using moderator analyses extending the analyses described above. The models will be extended to include the main effect of measures of high risk status, including higher prescription opioid doses, co-occurring benzodiazepine use, poor social support, and low readiness for change, together with the interaction effect of these terms with the intervention group factor. If the inclusion of a given interaction term in a model yields significantly better model fit, this provides evidence for moderation. Data plots and the estimated regression coefficients for the intervention, the moderator, and their interaction will explain the nature of the moderating effect.

d. Mediation analyses. We will address Hypothesis 4 through mediation analyses, with changes in readiness for change, self-efficacy, and coping as mediators. Here, we will follow the methods described in (105) First, to address the time course of these mediators separately from outcome, we will use the same mixed effects model approach described above. Second, to address whether these mediators predict later risky alcohol use, we will conduct a further series of mixed effects model analyses, using lagged versions of the mediator variables as time-varying covariates, together with the intervention and the other explanatory variables described above. We expect that the intervention effects on the mediators and on the outcomes will occur gradually over time, so we will use a latent growth curve mediation model to address the joint behavior across time. As suggested by MacKinnon, we will also examine the fit of other types of models, to obtain a more complete assessment of the intervention's direct and indirect effects on outcomes.

e. Missing values. The mixed effects models will provide valid estimates of treatment efficacy if the missing data meet the ignorable missingness assumption. We will conduct further analyses to assess the sensitivity of our inferences to possible violations of this assumption. First, we will use pattern mixture models (104), defining a categorical variable describing the main patterns of missing data, and including it as a main effect and interaction effect with intervention group in the modes for primary outcomes. Significant differences in the estimated intervention effects across levels of the pattern variable suggest one type of non-ignorable missingness. Second, shared parameter models (104) assume that the repeated responses and repeated binary indicators of missingness have possibly correlated random effects, and significant correlation indicates possible non-ignorability. Finally, semiparametric regression models (106) use inverse probability weighting to extend the validity of GEE models, and provide a different type of sensitivity analysis for the mixed effects models. All three approaches require certain model assumptions, so we will compare the results of the analyses over a range of such assumptions.

X. **Privacy and Confidentiality** (*Privacy refers to persons and to their interest in controlling the access of others to themselves.) (Confidentiality refers to protecting information from unauthorized disclosure or intelligible interception.) (Investigator should contact the Privacy Officer for additional details.)*

1. **Indicate the type of data that will be received by the Principal Investigator. Check all that apply.**

- 1.1.  De-identified – Without any identifiers that could link the data to a specific participant. (Contact Privacy Officer for assistance. If data is coded, it is not considered de-identified.)
- 1.2.  Identified – Linked to a specific participant by identifiers sufficient to identify participants. (See [HIPAA](#) and [Common Rule](#) Criteria for list of identifiers.)
- 1.3.  Coded – Linked to a specific subject by a code rather than a direct identifier. If coded is checked, specify:
  - 1.3.1 Explain who will maintain the link or code. **The research coordinator will maintain the link/code. Codes will be assigned during the initial screening phone call. The spreadsheet linking Veteran data to the code will be located on our secure study drive. Thus all data collected from screening onward will be protected by the code.**
  - 1.3.2 Describe who will have access to the link or code. **Research staff will have access to the codes.**
  - 1.3.3 Provide exact details for how the data is coded. **Participants will have a subject identification number that is a four digit number. We will use numbers sequentially, beginning with 1001.**

2. **Does the project require the use of existing Protected Health Information (PHI) from a database, medical records, or research records?  YES  NO  N/A**

- 2.1. If yes,
  - 2.1.1. Specify the source of the existing PHI **VISTA Pharmacy and MHA records. (The Mental Health Assistant (MHA) is a software package for VistA. MHA was developed to create an effective and efficient tool for mental health clinicians and their patients to use for the administration and scoring of assessment instruments and interviews that are not available elsewhere in CPRS or VistA)**
  - 2.1.2. Indicate the specific data elements/identifiers (e.g., name, address, phone numbers, etc.) on the below table. **Name, address, phone number, opiate prescription status.**
- 2.2. If the study uses an existing database/data warehouse,
  - 2.2.1. Provide a description of the database/data warehouse.
  - 2.2.2. Make clear who is responsible for maintaining it.
  - 2.2.3. Cite any relevant Standard Operating Procedures (SOP) for the database/data warehouse.
  - 2.2.4. Provide a copy of the SOP.

3. **Will PHI be collected prior to obtaining informed consent?  YES  NO  N/A**

- 3.1. If yes, complete and provide a HIPAA Waiver of Individual Authorization for Disclosure of Protected Health Information with this submission.

4. **HIPAA Identifiers - Indicate the PHI that will be collected from project participants directly or indirectly.**

- 4.1.  Name
- 4.2.  All geographic subdivisions smaller than a State, including street address, city, county, precinct, zip code, and their equivalent geocodes, except for the initial three digits of a zip code if, according to the current publicly available data from the Bureau of the Census
- 4.3.  All elements of dates (except year) for dates directly related to an individual, and all ages over 89 and all elements of dates (including year) indicative of such age, except that such ages and elements may be aggregated into a single category of age 90 or older.
  - 4.3.1.  Birth Date  Date of Death

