- 2.2. Describe how randomization or other treatment assignment will be made. **Veterans who meet criteria for participation will be randomly assigned to one of the two treatment conditions. Urn randomization will be used to balance the groups on three factors: gender, benzodiazepine or other drug use, and age. We will also be blocking on whether the person admits use or not when we do the randomization, so we get equal numbers of non-users in each condition. Urn randomization is a kind of biased-coin randomization where probability of being assigned to a group decreases if the group is overrepresented and increases if the group is underrepresented. As the sample size increases, the randomization shifts from perfect balance to complete randomization.**
- 2.3. For retrospective research studies, provide the "look-back" period. (e.g., December 1, 1999 through December 31, 2008.) **n/a**

3. **Study Duration**

- 3.1. Provide the estimated length of time to enroll all subjects and complete the study. **2.5 years of enrollment, but 5 years total for study start up, enrollment, completion, and analyses.**
- 3.2. Explain the expected duration of subject participation including any follow-up. **18 months for patients enrolled prior to 4/1/2019; 12 months for patients enrolled after 4/1/2019**
- 3.3. Specify the projected date of completion of the proposed study. **5 years from date of funding.**

4. **Drug Information** (If not applicable state, "Not Applicable.") **Not Applicable**

- 4.1. Specify if the drug or biological agent is:
  - 4.1.1. FDA approved
  - 4.1.2. Used for off-label purposes
  - 4.1.3. Not yet FDA approved.
- 4.2. Include the FDA Investigational New Drug (IND) number for all non-FDA approved and off-label drugs, biological agents or nutritional supplements. If not applicable state, "Not Applicable."
- 4.3. Provide all relevant information about the drug
- 4.4. Explain any wash-out periods, rescue medications permitted and any type of medications not permitted while enrolled in the study.
- 4.5. Describe blinding and un-blinding procedures.

- 4.6. Include the dosage, route of administration, previous use, and the safety and efficacy information on any drug used for research purposes.
- 4.7. Describe rationale for the dosage in this study.
- 4.8. Justify why the risks are reasonable in relation to anticipated benefits and/or knowledge.
- 4.9. Describe where drug preparation will be done.

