#### **Study visits:**

In addition to the intervention, all participants will be seen at 3, 6, 9, 12, and 18 months post baseline for research follow ups. Participants enrolled after 4/1/2019 will only be seen at 3, 6, 9, and 12 months post baseline for research follow ups. These will be done at the CMCVAMC and will take approximately 1.5 hours. The schedule of assessments (all of which are for research purposes only and not part of standard care) is as follows: SCID and MINI (B); Blood samples (%dCDT and GGT) (B and 18m); Time Line Follow-Back, SIP (B, 3, 6, 9, 12, 18); Drug urine toxicology tests (B, 3, 6, 9, 12, 18); Self-efficacy, Coping, Social Support, Readiness to Change, pain, depression, quality of life (B, 3, 6, 9, 12, 18).

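### The primary model omits baseline drinking and the randomisation factors: the test stays valid, but precision already paid for is given away

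*Combined protocol and SAP*

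**What the plan says.** Section W.4.2.a takes five repeated yes/no responses per person, all at follow-up, and fits a mixed effects logistic model: "The main explanatory variable will be a binary factor indicating intervention group, together with terms for time trends". Group by time is added if appropriate. Baseline drinking is therefore neither a covariate nor a response.

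Section M.2.2 describes the allocation: "Urn randomization will be used to balance the groups on three factors: gender, benzodiazepine or other drug use, and age". It then adds a fourth factor: "We will also be blocking on whether the person admits use or not when we do the randomization".

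The visit schedule in section O.1 collects the TLFB, the source of the primary outcome, at baseline as well as at each follow-up: "Time Line Follow-Back, SIP (B, 3, 6, 9, 12, 18".

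No other section adds these variables to the primary model. The secondary outcomes in W.4.2.b inherit the same choice: "The explanatory variables, time trends, and covariance structure for these secondary analyses will be chosen as described for the primary hypothesis". Benzodiazepine use appears in a model only for the moderator analyses of W.4.2.c: "The models will be extended to include the main effect of measures of high risk status".

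**The concern.** Baseline drinking is a natural candidate predictor of later drinking, and the trial already pays to collect it. If it is prognostic, leaving it out widens the confidence interval for the group effect and lowers power. Factors balanced by design raise a related issue. If they are prognostic and omitted, the standard error is overstated and the test is slightly conservative.

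This trial has little margin. The March 2018 Amendment cut the target to 150 drinkers plus 50 non-drinkers, against its own stated need of 136 to 162. At the upper end, 150 is 12 short.

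There is also a prespecification issue. If covariates may enter later, they could be chosen after results by group are known. Section W.1 plans two interim analyses, at 50% and 75% accrual, that can stop the study on a difference between groups.

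**Working it through.** **1. Reproducing the plan's power statement (W.4.1).** Inputs: 150 per group, 20% dropout, 80% power, five visits, alpha 5% (W.1; two-sided assumed), and "On the assumption of a within subject correlation of 0.3 (resp. 0.4, 0.5". The usual two-proportion sample size is multiplied by (1 + (m − 1)ρ)/m with m = 5. With 150 × 0.8 = 120 evaluable per group, the rates detectable against 30% are 19.7%, 18.8% and 18.1%. These round to the stated 20%, 19% and 18%. Using the rounded rates literally, power is 77.1%, 78.6% and 80.5%.

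**2. Cost of omitting baseline drinking, closed form.** For a baseline measure with correlation r to each of m equally correlated follow-ups:

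- R² = m r² / (1 + (m − 1)ρ)
- extra participants needed without adjustment = 1/(1 − R²) − 1

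The documents do not give r, so it is an assumption and is shown as a range. Example with m = 5, ρ = 0.3, r = 0.15: R² = 5 × 0.0225/2.2 = 0.051, so the cost is 5.4%.

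| r | m | ρ = 0.3 | ρ = 0.4 | ρ = 0.5 |
|---|---|---|---|---|
| 0 | 5 | 0% | 0% | 0% |
| ρ/4 | 5 | 1.3% | 2.0% | 2.7% |
| ρ/2 | 5 | 5.4% | 8.3% | 11.6% |
| ρ | 5 | 25.7% | 44.4% | 71.4% |
| ρ/2 | 4 | 5.0% | 7.8% | 11.1% |
| ρ | 4 | 23.4% | 41.0% | 66.7% |

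Four visits applies to participants enrolled after 4/1/2019. At r = ρ/2 and m = 5, R² is 0.051 to 0.104. On 150 participants that is 150 × R², about 8 to 16 people. If the adjusted analysis had 80% power, the unadjusted one would have Φ(2.80√(1 − R²) − 1.96), which is 77.9% at ρ = 0.3 and 75.5% at ρ = 0.5. An expected-information calculation for the random-intercept logistic model itself, with a binary baseline covariate at r = ρ/2, gives 5.0-5.3%, 7.8-8.3% and 10.9-11.8%.

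**3. The amended calculation.** The 2018 figures state no correlation. For 35% versus 20% with five visits, the same formula gives totals of 121, 143 and 165 at ρ = 0.3, 0.4 and 0.5 without loss. Solving for the stated 136 and 162:

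| Loss | Implied ρ | Extra N, r = ρ/2 | Extra N, r = ρ |
|---|---|---|---|
| none | 0.37-0.48 | 7-11% | 37-66% |
| 10% | 0.30-0.41 | 6-9% | 27-47% |
| 20% | 0.24-0.34 | 4-6% | 18-32% |

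**4. Why not a yes/no baseline indicator.** With an average follow-up prevalence of (35% + 20%)/2 = 27.5%, the correlation between a baseline and a follow-up indicator is capped. The cap is √[(0.275/0.725) × (1 − b)/b], where b is the proportion risky at baseline. If b = 80% the cap is 0.31, worth at most 19-28% extra N. If b = 95% it is 0.14, worth at most 3-5%. A quantity of drinking avoids this ceiling.

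**5. Simulated power.** Settings: 75 drinkers per arm, 35% versus 20%, five visits, dropout rising to 20%, 2,000 replicates per setting. The full model adds log(1 + baseline drinks), gender, age and drug use. The last three are set uninformative (10% women and 30% drug use assumed). Baseline strength here is a latent correlation relative to the follow-up one.

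| Baseline strength | ρ = 0.3: unadjusted → full | ρ = 0.4: unadjusted → full |
|---|---|---|
| Uninformative | 85.2% → 84.8% | 78.2% → 78.6% |
| Half | 84.0% → 86.4% | 79.0% → 83.9% |
| Equal (best case) | 84.7% → 94.4% | 79.7% → 95.8% |
| Half, plus 50 non-drinkers and the block | 78.3% → 81.7% | 72.5% → 77.6% |

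The last row assumes 5% risky drinking in non-drinkers in both arms and no effect in them. Monte Carlo standard error at half strength is about 0.8 to 1 point. Rejection under no effect at half strength was 5.3% and 4.9% unadjusted, and 5.7% and 5.1% with the full model.

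**6. Direction of the error for balanced factors.** If balanced factors explain R² of the outcome and are omitted, the true two-sided level is 2Φ(−1.96/√(1 − R²)): 4.4% at R² = 0.05 and 3.9% at R² = 0.10. Type I error is not inflated.

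**The case against.** **The size is unknown and half strength is arbitrary.** This stands. At a quarter of the follow-up correlation the cost is only 1.3-2.7%, and it may be zero. The range is what the documents allow.

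**The 0.3-0.5 belongs to a superseded calculation.** This stands in part. The amended 136 and 162 also match four visits, the unpooled formula, correlations of 0.2 and 0.3, and division by 0.8: 135.2 and 160.5, rounded up per arm to 136 and 162. At half strength that implies 2.6-5.0% extra participants, and 11-23% if equal. The match is not unique. It lowers part of the range but does not change the recommendation.

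**Half strength means different things in the two calculations.** True. The closed form halves a correlation with the binary outcome; the simulation halves a latent correlation with a drink count. The simulation therefore shows more, 8% and 12% extra N at ρ = 0.3 and 0.4, against 5% and 8%. It is closer to the covariate proposed here.

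**The simulated 150 is only one target.** Section R.1 adds to 115 + 60 = 175, or 125 drinkers after removing 50 non-drinkers. The simulation also gives everyone five visits. Its power values hold only under those settings.

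**Nothing is quantified for gender, age, drug use, the block or the secondary outcomes.** Correct. The case for these rests on matching the analysis to the allocation and on prespecification.

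**Calling group the main explanatory variable leaves room for covariates.** It may, but any covariates would then be unnamed and open to choice after the data are seen.

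The unstated role of baseline GGT and %dCDT is missing detail and carries no weight here.

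**Conclusion.** The concern holds. The primary model names neither the randomisation factors nor baseline drinking, although all are available before randomisation. Their omission does not invalidate the test. That statement covers this omission only, not the data-driven choice of time and covariance terms or the interim looks.

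The cost is imprecision of a size the documents do not fix: none if baseline is uninformative, about 5-12% more participants at half a follow-up correlation of 0.3-0.5, and more if stronger. In simulation the fuller model cost no detectable power when baseline was uninformative. At half strength it gained 2.4 to 4.9 points in 150 drinkers. The change should be made as an inexpensive improvement. Confidence is medium, because the gain depends on a correlation that must be assumed.

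**What to change.** Before any data are compared by group, including at the interim analyses, state in W.4.2.a that the primary model contains these fixed effects:

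- log(1 + baseline drinks per week) from the TLFB
- gender
- age, linear
- benzodiazepine or other drug use
- the admitted-use block, where both levels are analysed

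Give a rule for missing baseline values. In W.4.2.b, add each repeatedly measured secondary outcome's own baseline value to its model. Report a standardised (marginal) risk difference beside the adjusted odds ratio.

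The cost is a text change, four or five degrees of freedom, and code for the standardised difference; no new data are collected. The downside is that the adjusted odds ratio is conditional and not on the same scale as the unadjusted one, which is why the risk difference is needed. If an interim comparison by group has already been made, say so and report the unadjusted model as well.
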